Ventilatory days up to Day 28 [study date based on date/time]	
To derive the number of ventilatory days up to day 28, count the days for which the subject was intubated (from the CRF Form: "Extubation Summary") starting from the date of first IMP intake up to day 28 date, where Day 28 date = Day 1 date/time + 28 days.
 
In case of multiple periods of IMV during the first 28 days, the total duration of ventilation considered all periods of ventilation during the index admission.
 
Between the extubation and the subsequent intubation, there should be $\geq 48h$: if between the extubation and the subsequent intubation there is less than 48h, the extubation (from a clinical point of view) is considered unsuccessful, and it will be considered as a single intubation period (therefore that extubation period should not be considered in the calculation).
 
As all subjects are intubated at the beginning of the study the calculation will be:
 
Time from date/time of first IMP intake to first extubation date/time +
 
Time from second intubation to second extubation (if from first extubation and second intubation there are $\geq 48h$, otherwise Time from first IMP intake to second extubation) +
 
Time from third intubation to third extubation (if from second extubation and third intubation there are $\geq 48h$, otherwise Time from second intubation to third extubation) etc. up to day 28 date/time.
 
Note: the only possible range is the range of real number in the interval $[0, 28]$.

Primary endpoint "Ventilator free days (VFD) at day 28" [study day based on Date/time]	
Number of days from First IMP Intake to Day 28 date when the patient will be alive and free of invasive ventilation[^]. It will be derived as follows:
 
 - Patients who will die before or on day 28: VFD= 0*. - If patient is alive at Day 28 (last available day ≥ 26): VFD = 28 – Ventilatory days up to Day 28 - If subject is alive and followed for < 26 days (last available date < 26) the endpoint is set as missing. 
[^] intubation/extubation status at day 28: check intubations in "Extubation Summary" CRF form.
 
The only possible range of values is between 0 and 28.
 
*In the case subjects are never been extubated: VFD = 0

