All-cause mortality by day 28 and by day 60 [study day based on Date]	
The following algorithm is implemented.
 
Death at day 28:
 
If patient died up to Day 28* (included) then endpoint = "Y"
 
Else if Last available day\geq26* then endpoint = "N"
 
Else If Last available day$<$26* endpoint is missing.
 
Death at day 60*: use the time window (+/-2)
 
If patient died up to Day 60* (included) is endpoint = "Y"
 
Else if Last available day\geq58* then endpoint = "N"
 
Else If Last available day$<$58* endpoint is missing.
 
*Day 28= Day1 (date 1st IMP intake) + 27; similar derivation for day 26, 60, 58 mentioned above

Standard/Forms/Template				
Title		Statistical Analysis Plan Template		
Code		Version	Effective Date	Page
PPD		01	29 Aug 2022	74 of 78

Parameter	Calculation

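### The SAP's ventilatory-days formula contradicts the 48-hour merge rule in its own row and, if programmed literally, gives a wrong co-primary VFD for some Day-28 survivors

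*SAP*

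**What the plan says.** VFD at day 28 is one of the two co-primary endpoints (SAP 3.5.1 and 4.1). Under SAP 11.1.1 a patient alive at day 28 scores 28 minus ventilatory days, and a patient who dies by then scores 0.

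The row for ventilatory days describes the count twice. The prose says to "count the days for which the subject was intubated". It adds that when reintubation follows within 48 h the extubation was unsuccessful, and "it will be considered as a single intubation period (therefore that extubation period should not be considered in the calculation".

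The row then sets the calculation out as a sum:

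- The first term is "Time from date/time of first IMP intake to first extubation date/time", with no condition attached.
- The second term is the second intubation period if the gap before it is 48 h or more, "otherwise Time from first IMP intake to second extubation".
- The third term follows the same pattern: the third period if the gap is long enough, "otherwise Time from second intubation to third extubation".

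The row ends by stating that "the only possible range is the range of real number in the interval" 0 to 28. The VFD row repeats those limits for VFD.

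On the time limit, the ventilatory-days row has "where Day 28 date = Day 1 date/time + 28 days". The all-cause mortality row has "Day 28= Day1 (date 1st IMP intake) + 27".

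**The concern.** Two rules in one row, for one co-primary endpoint, give different numbers. A programmer who follows the prose merges the periods. A programmer who codes the displayed sum counts the earlier period again, because the under-48 h branch restarts the clock at the beginning of a period that is already in the total.

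The error always lowers VFD, and reintubation happens after randomization, so it need not balance between arms. The stated range would expose only the extreme cases; most wrong values would look plausible. The VFD row gives no rule for negative results, whereas the ICU-free days row sets them to 0. Flooring VFD in the same way would score some survivors the same as deaths. Without flooring, the supplementary log analysis, which adds 0.5 to VFD (SAP 7.1.3.4), would be undefined at a value such as -4. VFD values of retrieved dropouts also inform the imputation model (SAP 7.1.1.2), so an error there could reach imputed patients.

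**Working it through.** **Inputs.** All are from the ventilatory-days and VFD rows of SAP 11.1.1. Let E1, E2, E3 be the extubation times and I2, I3 the reintubation times, in days from first dose and cut at 28. A gap under 48 h is a gap under 2 days. The SAP has no worked example; the only figure to check against is the 0 to 28 range. The timelines below are illustrations, not trial data.

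**Three ways to compute ventilatory days.**

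- *Literal sum*: E1 + T2 + T3. T2 = E2 - I2 if I2 - E1 is at least 2, otherwise E2. T3 = E3 - I3 if I3 - E2 is at least 2, otherwise E3 - I2.
- *Merge rule* (the prose): join periods separated by less than 2 days, then add each joined period once.
- *Replacement reading*: as the literal sum, but an under-48 h branch replaces the term before it instead of being added.

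| Intubated (days from first dose) | Literal sum | Merge rule | Replacement reading |
|---|---|---|---|
| 0-6, 9-14 | 6 + 5 = 11, VFD 17 | 11, VFD 17 | 11, VFD 17 |
| 0-5, 6-10 | 5 + 10 = 15, VFD 13 | 10, VFD 18 | 10, VFD 18 |
| 0-12, 13-20 | 12 + 20 = 32, VFD -4 | 20, VFD 8 | 20, VFD 8 |
| 0-5, 9-12, 13-16 | 5 + 3 + 7 = 15, VFD 13 | 5 + 7 = 12, VFD 16 | 12, VFD 16 |
| 0-5, 6-9, 10-13 | 5 + 9 + 7 = 21, VFD 7 | 13, VFD 15 | 7, VFD 21 |

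**What the table shows.**

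- With gaps of 48 h or more (first line) all three agree.
- If only the first extubation fails, the literal sum is too large by E1: 5 days in the second line, 12 in the third. The third line breaks the stated range.
- If only the second fails, it is too large by E2 - I2: 12 - 9 = 3 days in the fourth line.
- If both fail, it is too large by E1 + E2 - I2: 5 + 9 - 6 = 8 days in the fifth line. The replacement reading is then too small by I2 = 6 days, so its error runs the other way.

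**Possible size in an arm.** The documents give no rate of reintubation within 48 h. As an assumption, suppose 5% to 20% of an arm are Day-28 survivors whose first extubation fails in this way, with a mean first period of 5 to 14 days. The arm mean VFD would then fall by between 0.05 x 5 = 0.25 and 0.20 x 14 = 2.8 days before any flooring. For scale, the planned one-sided interval width for VFD is 3.75 days (SAP 3.3).

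**Day 28.** For a first dose on the 1st of a month, the date-based rule puts Day 28 on the 28th (1 + 27). The ventilation window runs into the 29th (1 + 28). The VFD death rule does not say which of the two it uses.

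**The case against.** The best defence is that the row already states the intended quantity. The prose comes before the formula, says that a short gap makes one period, and bounds the result at 0 to 28. The under-48 h branches sit in parentheses and restart at the beginning of the preceding period, which suggests that they were meant to replace that period's term. Read so, the formula agrees with the prose for any single failed extubation. On this view the row is loosely written and the endpoint is sound.

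Much of that stands. A reader might infer that the trial's VFD results are wrong. The documents do not support this: they show conflicting instructions, not the program. Nor is every patient with a failed extubation affected. Deaths by day 28 score 0 whatever the sum gives, and gaps of 48 h or more are computed correctly. What does not stand is that the replacement reading rescues the formula, because it gives 7 days instead of 13 after two consecutive failures. No reading of the sum considered here matches the prose in every case.

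A reader might also infer that the two Day 28 definitions are an error that makes VFD and mortality contradict each other. That goes too far. A window of 28 x 24 h is what 28 minus ventilatory days needs in order to reach 0 for a patient ventilated throughout. Mortality follows the general date rule of SAP 3.2.1. Only the date of death is collected, and for OI the SAP therefore uses the date-based day (SAP 4.4.1). If VFD does the same, it agrees with mortality. What remains is an ambiguity about deaths on one calendar day.

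**Conclusion.** The concern holds as an internal contradiction in the derivation of a co-primary endpoint. Followed literally, the sum counts the preceding period twice whenever reintubation comes less than 48 h after extubation. It can also leave the SAP's own range. VFD is wrong only if the formula is programmed as written, and then only for patients alive at day 28 with such a gap. For one patient the error can be large: 5 and 12 days in the two-period examples. The trial-level effect is unknown; the range of 0.25 to 2.8 days in an arm mean rests entirely on assumed rates and durations. The row should be corrected because the endpoint is co-primary and most wrong values would pass a range check. The Day 28 point is a separate, minor clarification.

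**What to change.** Replace the formula in the ventilatory-days row with: merge consecutive intubation periods separated by less than 48 h, then sum each merged period once, from first IMP intake, cut at first IMP date/time + 28 days.

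Check the VFD program, including any version already written, against test cases with a known answer. These should cover one failed extubation, two in a row, a gap of 48 h or more followed by a short one, and a reintubation that lasts past day 28. For the last, intubation over 0-10 and from 11 to beyond 28 should give 28 ventilatory days and VFD 0; the literal sum gives 10 + 28 = 38.

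Separately, keep the 28 x 24 h window for ventilation duration and state that the death rule inside VFD uses the date-based Day 28 (Day 1 date + 27), as mortality does. Applying + 27 to the ventilation window as well is not advisable, because it would shorten the period from which VFD is subtracted.

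The cost is one rewritten SAP row, one added sentence and a short program check. Data collection, sample size and the analysis model do not change.

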10.3.2 RETROSPECTIVE SUBJECT INFORMED CONSENT

Subjects for whom consent was given by a legally authorized representative will be informed of their participation in the study by the Investigator. This process will take place once the subject has regained the capacity to understand the details of the study. The timing of this process will thus vary between subjects. However, every attempt to obtain retrospective consent must be made when the subject's condition is appropriate. Once informed, subjects will be given an adequate amount of time to consider their decision to consent to continued participation in the study and to sign an ICF.

If the consent has been given by the legally authorized representative, the subject should be informed about their participation in the study and should have the opportunity to confirm or revoke their consent. If the subject does not give retrospective consent, then the subject will be asked if the data collected to that time point can be analyzed. If the subject does not allow any of their data to be used, then the data collected from the subject until that time point will not be entered into the analyses and no further data will be collected; the

subject will be considered as withdrawn and the reason for withdrawal will be “retrospective consent not given”.

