Estimand #1: Difference in means between Reparixin and Placebo in the change in oxygenation index (OI) from baseline to Day 7 in adult patients hospitalized for Acute Respiratory Distress Syndrome, as defined by the inclusion-exclusion criteria of the study, regardless of treatment discontinuation whatever the reason and alive up to day 7, intubated at Day 7.

The primary estimand #2 is defined by the following:

- Population: Adult patients hospitalized for Acute Respiratory Distress Syndrome, as defined by the inclusion-exclusion criteria of the study.
- Variables: Ventilator free days (VFD) at day 28.
- Intercurrent events:
 - Death before or on Day 28, as a terminal event which precludes the complete observation of the variable, will be handled by the composite strategy. The event will be included in the estimand with an extreme unfavorable value (0) characterizing the treatment failure.
 - Treatment discontinuation, which may affect interpretation of the variable, will be handled by the treatment policy strategy. The occurrence of the intercurrent event will be irrelevant. All observed values will be used regardless of occurrence of the

Standard/Forms/Template				
Title		Statistical Analysis Plan Template		
Code		Version	Effective Date	Page
PPD		01	29 Aug 2022	29 of 78

intercurrent event. Retrieved dropouts will be used for data imputation of all missing data (not due to death), whichever is the reason of missingness.

- Population-level summary: Mean VFD at day 28.

Estimand #2: Difference in means between Reparixin and Placebo in Ventilation Free Days (VFD) at Day 28 in adult patients hospitalized for Acute Respiratory Distress Syndrome, as defined by the inclusion-exclusion criteria of the study, regardless of treatment discontinuation whatever the reason and alive at day 28.

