1. Missing data at Day 28 will be imputed using the specified MI regression model. According to MI-RD approach, only non-missing values from retrieve dropouts will be used to inform the MI regression model. A total of 1000 datasets will be created. These datasets will be utilized in Step #2.
2. Each of the 1000 dataset with observed and imputed data will be analyzed using the ANOVA model. Rubin's rule will be used for combining results to draw inference.

If there are not enough retrieved dropouts for convergence of MI-RD regression model, the Copy Reference approach will be used using gender and age class (<65, >=65 years) as covariates. Imputation of values in the two treatment arms will be done using the non-missing values from all the patients in the control group. The final decision on the use of the MI-RD vs Copy-Reference will be done at the time of the analysis and reported in the CSR.

The difference between Reparixin and placebo at Day 28 will be displayed together with the corresponding two-sided 90% confidence interval (in order to reflect the one-sided 95% confidence intervals). One-sided p-value (alpha=0.05 one-sided) will also be displayed for descriptive purpose.

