Last available date	
Most recent visit date/assessment date/procedures date (max: end of study date) defined as follows.
 
last available date = end of study (EOS) date*
 
If reason for discontinuation = “Lost to follow-up”, last available date=most recent visit date§ or assessment date^ or procedures date
 
*For patient who dies: end of study date = date of death
 
§ at Day 60 visits to be considered only if patient Vital Status = “Alive” in the form “Follow-Up”
 
^assessment including information from all summary pages (AEs, CM...)

Last available day	
Last available date – Day 1 date + 1
 
Note: Day 1 date for derivation of the Last available day is based on calendar day (i.e., date of first IMP)

Time from Date of diagnosis of moderate to severe ARDS to randomization	
Randomization date – Date of diagnosis of moderate to severe ARDS + 1.
 
CRF field: “Date of diagnosis of moderate to severe ARDS as defined in inclusion criterion 3” in “ARDS-SPECIFIC INFORMATION” CRF form

Extent of exposure (hours)	
Exposure calculated as total number of hours under treatment: (Date:time of last administration of IMP – Date:time of first administration of IMP)
 
Date/time first and last administration defined in SAP 3.1.1
 
Date/time first administration of IMP missing:
 
If Date first administration of IMP is not missing and time first administration of IMP is missing then:
 
If Date first administration of IMP = “Date of Randomization” and Time randomization is not missing then time first administration of IMP= time of randomization;
 
Otherwise set time first administration IMP = “00:00”
 
Date/time last administration missing:
 
If Time last administration of IMP is missing then set time last administration IMP = “23:59”

Total number of tablets scheduled during the treatment period	
[ROUND(Extent of exposure (hours)/8) + 1]*2
 
The result has to be taken rounded to the closest integer.

Extent of exposure (days)	Date of last administration of IMP – Date of first administration of IMP + 1.

Standard/Forms/Template				
Title		Statistical Analysis Plan Template		
Code		Version	Effective Date	Page
PPD		01	29 Aug 2022	59 of 78

Parameter	Calculation

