Retrieved drop-out flag for ventilatory free days at day 28	
For "VFD at Day 28" the retrieved dropouts are the patients that discontinued the study treatment (treatment completers/discontinuers are defined above in this table under "Treatment completed/discontinued") and have the endpoint evaluable by Day 28 (death on the day of the treatment discontinuation not part of the retrieved dropout):
 
Set to 'Y' if Subject discontinued the treatment prematurely and patient is alive or have date of death after end of treatment, and the endpoint is not missing for this parameter and timepoint.

Standard/Forms/Template				
Title		Statistical Analysis Plan Template		
Code		Version	Effective Date	Page
PPD		01	29 Aug 2022	63 of 78

Parameter	Calculation
Change in oxygenation index (OI) from baseline to day 4 [study day based on Date/time]	
The endpoint is derived similarly to change from baseline at day 7.
 
 - If patient dies before Day 4, or at Day 4 (Day 4 date = Day 1 date + 3, since only date of death -no time- is collected) and OI is missing: OI at day 4 = 90th percentile of the distribution of the primary variable at Day 4. - If patient at Day 4 is extubated* and OI is not evaluable (i.e., if the patient results not intubated* in the time range [First IMP Intake Date/Time +60h, First IMP Intake Date/Time +83h and 59 min]), OI at day 4 = 10th percentile of the distribution of the primary variable at Day 4. - Otherwise, OI is set to missing. 
*intubation/extubation status at day 4: check intubations in "Extubation Summary" CRF form. Use the multiple entries of extubation/re-intubation: if the last record of intubations/extubations prior day 4 is an extubation, and there are no intubations at day 4, it means the subject was extubated on Day 4.

ICU stay up to Day 28 and up to hospital discharge (days)	The information on ICU length of stay is collected under "Other Clinical Event Form" at Day 28 Visit and at Hospital Discharge Visit

Standard/Forms/Template				
Title		Statistical Analysis Plan Template		
Code		Version	Effective Date	Page
PPD		01	29 Aug 2022	64 of 78

Parameter	Calculation

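### VFD for survivors whose follow-up ends before Day 26 is imputed without using their recorded ventilator history

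*SAP*

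**What the plan says.** SAP 11.1.1 derives VFD as 28 minus ventilatory days for a patient alive with last available day 26 or later, and as 0 for death by Day 28. For other survivors: "If subject is alive and followed for < 26 days (last available date < 26) the endpoint is set as missing". Ventilatory days come from dated entries in the Extubation Summary form. The last available date is normally the end-of-study date; for a patient lost to follow-up, "last available date=most recent visit date§ or assessment date^ or procedures date".

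Estimand #2 (SAP 4.4.1) sets the source of imputation: "Retrieved dropouts will be used for data imputation of all missing data (not due to death), whichever is the reason of missingness". In SAP 7.1.1.2 the model contains treatment, gender and age class, and "only non-missing values from retrieve dropouts will be used to inform the MI regression model". If too few retrieved dropouts are available for convergence, Copy Reference draws on all placebo patients with a value, using gender and age class.

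The VFD donor flag reads: "Set to 'Y' if Subject discontinued the treatment prematurely and patient is alive or have date of death after end of treatment", provided VFD is not missing. The treatment-completion rule in the same table counts a patient whose drug ended on discharge home as a completer, so such a patient cannot be a donor.

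**The concern.** When follow-up stops early, VFD is only partly unknown. The record fixes how many ventilated days have already accrued and whether the patient was off the ventilator at last contact. The plan treats such a patient as if nothing were known beyond arm, sex and age class.

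The donors are also a poor match for one important kind of recipient. Someone extubated, discharged home and then lost is imputed from patients who stopped the drug prematurely. That group leaves out discharged-home patients and includes those who died after stopping, scored 0 if the death was by Day 28. By contrast, estimand #1 treats extubation at Day 7 as a success for the oxygenation index.

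VFD is a co-primary endpoint in a trial of about 33 patients per arm, so a few badly placed values can move the estimate.

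**Working it through.** **Inputs.** From SAP 3.3: SD of VFD 8 days; stated precision 3.75 days (one-sided 95%); 60 evaluable; about 66 enrolled 1:1, so 33 per arm. The documents give no mean VFD, so these are assumptions: donor mean 5 to 10 (wider range 4 to 16), true VFD of an affected recovered patient 18 to 23 (wider 15 to 23), and normal draws with SD 8.

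**1. The plan's own figure.** 46.5% × 8 = 3.72 days, against 3.75 stated. A plain t half-width is 1.672 × 8 × √(2/30) = 3.45. Multiplying by √(χ² 80th percentile, 58 df / 58) = 1.073 gives 3.71. The stated figure is therefore reproduced if 80% assurance was intended; that level is inferred, not stated. It serves here only as a yardstick.

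**2. A recovered patient (illustrative).** Extubated at day 5, alive and off the ventilator at last contact on day 20, later contacts fail.
- Highest possible VFD: 28 − 5 = 23.
- Lowest if alive at Day 28 (reintubated straight after last contact): 28 − 5 − 8 = 15.
- Otherwise 0, if death occurred by Day 28.

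**3. A reintubated patient (illustrative).** Ventilated days 0 to 10, off days 10 to 14, ventilated again to last contact on day 24. Observed ventilated days: 10 + 10 = 20. Maximum VFD: 28 − 20 = 8.

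| Donor mean | P(draw < 15), patient 2 | P(draw outside 15–23), patient 2 | P(draw > 8), patient 3 |
|---|---|---|---|
| 4 | 0.92 | 0.92 | 0.31 |
| 8 | 0.81 | 0.84 | 0.50 |
| 12 | 0.65 | 0.73 | 0.69 |
| 16 | 0.45 | 0.64 | 0.84 |

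A general 0-to-28 limit would not cure patient 3. At donor mean 4, P(draw > 8 given 0 to 28) = (0.309 − 0.001)/(1 − 0.309 − 0.001) = 0.45. At donor mean 16 it is (0.841 − 0.067)/(1 − 0.023 − 0.067) = 0.85.

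**4. Effect on an arm mean.** Shift per extra affected patient in one arm = (donor mean − true VFD)/33.
- Smallest: (10 − 18)/33 = −0.24 days.
- Largest: (5 − 23)/33 = −0.55 days.
- Wider assumptions: (4 − 23)/33 = −0.58 to (16 − 15)/33 = +0.03, so the sign is not guaranteed.
- If the same number is affected in each arm, with equal true and donor means, the shifts cancel in the difference.

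**5. Do other analyses use the record?** The MAR analysis (SAP 7.1.2.1) keeps the same covariates and widens the donors to all patients with values. The complete-case analysis (7.1.3.1) drops these patients. The FAS and per-protocol analyses (7.1.3.2, 7.1.3.3) repeat the primary method. The log-scale analysis (7.1.3.4) changes only the scale, and 7.1.3.5 adds variables imbalanced at baseline. None uses ventilation observed after baseline.

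**The case against.** The strongest reply is that few patients meet the rule and that setting VFD to missing is right when they do. Much of this stands.

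- **Hospital discharge is not the trigger.** A reader might infer that leaving hospital early makes VFD missing. It does not. Note 19 to the schedule plans a Day 28 visit, or a phone contact covering ventilation, reintubation and mortality. A Day 60 call follows, with three attempts before a patient counts as lost (Protocol 6.1.3). A patient reached then has an observed VFD.
- **Retrospective consent.** A reader might cite Protocol 10.3.2, "subject will be considered as withdrawn and the reason for withdrawal will be", as a second route into the rule. Those words concern patients who refuse any use of their data, and such data leave the analysis. The section does not spell out follow-up for someone who declines but allows use.
- **Later events are unknown.** Death or reintubation after last contact would change VFD, so missing is defensible. Last available days 26 and 27 lie within the Day 28 visit window and are no precedent for carrying status forward from any day.
- **Never-extubated patients.** A footnote to the VFD row gives them 0, so a never-extubated patient lost on day 20 is no clear example of an impossible draw. The footnote and the missing rule overlap there.
- **Unbounded draws.** This cannot be claimed. The VFD row gives 0 to 28 as the possible range, and the SAS code section is not in the copy reviewed. A general limit may exist, but section 7.1.1.2 describes no patient-specific one.
- **Donors.** They may be placebo patients under Copy Reference, and drug stopping has many causes. With treatment in the MI-RD model, donors in a better arm may also score higher.

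What remains is that neither imputation route uses the ventilator record. The complete-case analysis removes the imputed values but does not use the record either.

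**Conclusion.** The point holds as an imputation weakness limited to survivors whose follow-up, not hospital stay, ends before Day 26. Their recorded ventilation history is ignored in the primary analysis and in every planned check.

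The illustrative size is 0.24 to 0.55 days on one arm's mean per extra affected patient, against a stated precision of 3.75 days. It rests on assumed donor means and true values and on an imbalance between arms.

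A reader might go further and conclude that the rule necessarily penalises the arm that recovers faster. The documents do not show this. Downward is the likely direction for recovered patients because of who can be a donor. But the donor mean is not given, reintubated patients can be scored too high, and equal effects in the two arms cancel. The trial is also descriptive, with no formal hypothesis test, so what is at stake is the accuracy of the estimate and its interval.

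**What to change.** Keep these values as missing, and amend SAP 7.1.1.2 and 11.1.1 as follows.

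- **(a) Patient-specific limits.** Restrict each draw to between 0 and 28 minus the ventilated days already observed for that patient, under both MI-RD and Copy Reference.
- **(b) Ventilation status.** Where the number of donors permits, add status (extubated or ventilated) as an imputation covariate, measured in donors at the study day of the recipient's last contact. Do not use donors' ventilated days to Day 28: in surviving donors, VFD is exactly 28 minus that number.
- **(c) Sensitivity analyses.** For patients discharged alive and off the ventilator, set VFD to 28 minus known ventilatory days in one analysis and to 0 as the worst case in another. Keep the current rule as a further sensitivity analysis. The 28-minus rule is a best case, so it should not become the primary rule.
- **(d) Overlapping rules.** State which applies to a never-extubated survivor lost before Day 26: the missing rule or the footnote giving 0.

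The data are already in the Extubation Summary form. The cost is SAP wording and extra programming, and (b) may meet convergence limits if donors are few.
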